2 SYNOPSIS OF STUDY DESIGN AND PROCEDURES

2.1 PURPOSE OF THE STATISTICAL ANALYSIS PLAN

This statistical analysis plan (SAP) is intended to provide a detailed and comprehensive description of the planned methodology and analysis to be used for the randomized component of Protocol 10-389, the EXCEL clinical study. This plan is based on Version 9.0 of the study protocol.

2.2 OBJECTIVE OF THE STUDY

The objective of the study is to establish the safety and efficacy of the commercially approved XIENCE Family Stent System (inclusive of XIENCE PRIME, XIENCE V, XIENCE Xpedition and XIENCE PRO [for use outside the U.S. [OUS] only]) in subjects with unprotected left main coronary artery (ULMCA) disease (either isolated to the left main trunk or associated with disease in other coronary arteries) by demonstrating that compared to coronary artery bypass graft surgery, treatment of the left main stenosis \pm other significant coronary lesions with the XIENCE stent will result in non-inferior or superior rates of the composite measure of all-cause death, myocardial infarction or stroke at the anticipated median follow-up of three years.

2.3 DESIGN OF THE STUDY

The randomized control portion of this study (that will be referred to as RCT) is a prospective, unblinded, randomized multicenter trial of approximately 1,900 subjects enrolled at approximately 165 US and OUS centers. Following diagnostic angiography demonstrating significant ULMCA disease and consensus of the local Heart Team (qualified participating interventional cardiologist and cardiac surgeon) that the subject meets the study entry criteria, subjects will be consented and randomized 1:1 to: a) PCI using XIENCE (N=950), or b) CABG (N=950). Follow-up for all randomized subjects will continue for five years with a potential for additional follow-up to 10 years. The primary endpoint will be assessed at least 2-years after the last subject is randomized, with a median follow-up duration in all subjects of at least 3 years.

All randomized subjects will have a follow-up telephone contact or office visit at 30 days, 180 days, and 1, 2, 3, 4 and 5 years following the index procedure. In addition, to minimize bias in the assessment of the primary endpoint, at the time the last randomized subject reaches the 2-year follow-up duration (730 + 28 = 758 days), an additional adverse event (AE) check will be performed in order for data up to 3 years (365 days*3=1095 days) from the date of randomization to be collected equally in both arms.

The AE check will commence the day after the 2-year follow-up duration of the last subject enrolled (i.e. 758 days), and will be completed prior to the database snapshot. At this time,

subjects with either of the following conditions should be contacted by each clinical site by phone or office visit to collect AE information:

- Subjects who have not yet completed the 3-year visit, unless the most recent follow-up was completed within 28 days of the AE check initiation; or
- Subjects who have completed a 3-year visit before day 1067 after randomization (i.e. >28 days prior to exactly 3 years [1095 days]).

For subjects who have completed any follow-up visit at \geq (1095 – 28= 1067) days, the AE check is not required.

An additional group of approximately 1000 consecutive subjects who are not eligible for randomization or for other reasons are not randomized will be consented for the Universal Registry. All patients with left main disease without prior CABG in whom the visual estimated diameter stenosis is greater than or equal to 50% will be eligible for the enrollment into EXCEL registry. These subjects will be consented for a Universal Registry, and followed until the time of initial treatment per standard of care with either PCI, CABG or medical therapy.

Approximately 100 consecutive subjects from the Universal Registry with a \geq 50% and <70% visually estimated angiographic diameter stenosis who otherwise meet all enrollment criteria, but without significant ischemia by noninvasive testing consistent with significant ULMCA disease, and in whom IVUS shows a MLA >6.0 mm² and/or have an FFR >0.80, will not be randomized but will be analyzed separately as intermediate lesion subjects, and followed until the time of initial treatment per standard of care with either PCI, CABG or medical therapy.

For PCI the study device is:

| $\begin{array}{l} \text{Diameter} \rightarrow \\ \text{Length} \downarrow \end{array}$ | 2.25 mm | 2.5 mm | 2.75 mm | 3.0 mm | 3.5 mm | 4.0 mm |
|--|---------|--------|---------|--------|--------|--------|
| 8 mm | Х | Х | Х | Х | Х | Х |
| 12 mm | Х | Х | Х | Х | Х | Х |
| 15 mm | Х | Х | Х | Х | Х | Х |
| 18 mm | Х | Х | Х | Х | Х | Х |
| 23 mm | Х | Х | Х | Х | Х | Х |
| 28 mm | Х | Х | Х | Х | Х | Х |

XIENCE V EECS Product Sizes

XIENCE PRIME EECS Product Sizes

| $\begin{array}{l} \text{Diameter} \rightarrow \\ \text{Length} \downarrow \end{array}$ | 2.25 mm | 2.5 mm | 2.75 mm | 3.0 mm | 3.5 mm | 4.0 mm |
|--|---------|--------|---------|--------|--------|--------|
| 8 mm | Х | Х | Х | Х | Х | Х |
| 12 mm | Х | Х | Х | Х | Х | Х |

| $\begin{array}{l} \text{Diameter} \rightarrow \\ \text{Length} \downarrow \end{array}$ | 2.25 mm | 2.5 mm | 2.75 mm | 3.0 mm | 3.5 mm | 4.0 mm |
|--|---------|--------|---------|--------|--------|--------|
| 15 mm | Х | Х | Х | Х | Х | Х |
| 18 mm | Х | Х | Х | Х | Х | Х |
| 23 mm | Х | Х | Х | Х | Х | Х |
| 28 mm | Х | Х | Х | Х | Х | Х |
| 33 mm | n/a | Х | Х | Х | Х | Х |
| 38 mm | n/a | Х | Х | Х | Х | Х |

XIENCE Xpedition Product Sizes

| $\begin{array}{l} \text{Diameter} \rightarrow \\ \text{Length} \downarrow \end{array}$ | 2.25 mm | 2.5 mm | 2.75 mm | 3.0 mm | 3.25 mm | 3.5 mm | 4.0 mm |
|--|---------|--------|---------|--------|---------|--------|--------|
| 8 mm | Х | Х | Х | Х | Х | Х | Х |
| 12 mm | Х | Х | Х | Х | Х | Х | Х |
| 15 mm | Х | Х | Х | Х | Х | Х | Х |
| 18 mm | Х | Х | Х | Х | Х | Х | Х |
| 23 mm | Х | Х | Х | Х | Х | Х | Х |
| 28 mm | Х | Х | Х | Х | Х | Х | Х |
| 33 mm | n/a | Х | Х | Х | Х | Х | Х |
| 38 mm | n/a | Х | Х | Х | Х | Х | Х |

XIENCE PRO Product Sizes

| Diameter → Length ↓ | 2.25 mm | 2.5 mm | 2.75 mm | 3.0 mm | 3.5 mm | 4.0 mm |
|------------------------|---------|--------|---------|--------|--------|--------|
| 8 mm | Х | Х | Х | Х | Х | Х |
| 12 mm | Х | Х | Х | Х | Х | Х |
| 15 mm | Х | Х | Х | Х | Х | Х |
| 18 mm | Х | Х | Х | Х | Х | Х |
| 23 mm | Х | Х | Х | Х | Х | Х |
| 28 mm | Х | Х | Х | Х | Х | Х |
| 33 mm | n/a | Х | Х | Х | Х | Х |
| 38 mm | n/a | Х | Х | Х | Х | Х |

2.3.1 Primary Endpoint

The primary endpoint is the composite measure of all-cause death, myocardial infarction (MI) or stroke (modified Rankin Scale (mRS) ≥ 1 and increase by ≥ 1 from baseline). measured by the Kaplan-Meier failure rate estimate at 3 years. For the primary analysis of the primary endpoint, this Kaplan-Meier rate will be defined from the date of randomization. All available data through 3-year follow-up will be used, but only events occurring up to day 1095 after randomization will be counted for the primary endpoint. For a sensitivity analysis, the Kaplan-Meier rate will be defined at the time of the index procedure date. Both of these analyses will be conducted at the time when approximately 50% of the patients have reached the 3-year follow-up AND all patients have reached the 2-year follow-up, whichever time point is latest.

For the primary and sensitivity analyses, days from the randomization date and procedure date to the first occurrence of one of the events within this composite, an early withdrawal date, or the last follow-up date will be calculated for each patient respectively. For patients who dropped out early, but had a death date available per the national death registry, this date will be used in the calculation of days (and will be counted as a primary endpoint event). If a patient does not have an event or an early withdrawal date:

- Days from randomization will be set to 1095 days (3 years) if their last follow-up date is known to occur after 3 years.
- The date of the last visit will be the date of the last phone call, office visit or medical contact.

The primary endpoint will first be tested for noninferiority with a margin of 4.2%. The critical value will be generated using the Com-Nougue¹ approach to estimating the Z-statistic with Greenwood's formula for estimating the standard error.

$$Z = \frac{F_{CABG}(T) - F_{PCI}(T) - \delta}{\sqrt{Var(F_{CABG}(T)) + Var(F_{PCI}(T))}}$$

Where, for each treatment group (CABG or PCI):

F(T) = Kaplan Meier estimator of failure at time T

 δ = non-inferiority margin

Var = variance of the estimator = σ^2 , where σ is defined as:

$$\sigma$$
 = standard error by Greenwood's formula = S(T=1095) $\sqrt{\sum_{j=1}^{1095} \frac{d_j}{n_j s_j}}$

S = 1 - F = KM estimate of survival at time T

n = number of subjects

d = number of events

s = n-d

The 95% CI for $F_{CABG}(T) - F_{PCI}(T)$ is then:

$$F_{CABG}(T) - F_{PCI}(T) \pm \mathbf{z}_{1-\alpha} \sqrt{Var(F_{CABG}(T)) + Var(F_{PCI}(T))}$$

P-value = 1- probnorm(Z)

Superiority testing of the primary endpoint will be performed using the same Z-statistic calculation that is defined above, without the non-inferiority margin. Statistical significance will be evaluated for both analyses at a 1-sided alpha level of 0.025.

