2.3.2 Major Secondary Endpoints

The primary analysis for these two powered secondary endpoints will be based on the analysis applied to the time from randomization estimate. Sensitivity analyses will be performed on the time from procedure estimate. There are two major powered secondary endpoints:

- Composite measure of all-cause mortality, MI or stroke (mRS≥1 and increase by ≥1 from baseline) presented as a Kaplan Meier rate defined from randomization to 30 days post randomization This is the same as the primary endpoint measured at 30 days. Two sets of analyses will be performed. Days from the randomization date or procedure date to the first occurrence of the one of the events within this composite, an early withdrawal date, or the last follow-up date will be calculated for each patient respectively. For patients who dropped out early, but had a death date available per the national death registry, this date will be used in the calculation of days (and will be counted as an event). If a patient does not have an event or an early withdrawal date then days from randomization will be set to 30 days if their last follow-up date is known to occur after 30 days. These KM estimates will be put into the Z statistic defined in Section 2.3.1 using a margin of 2% to test for non-inferiority.
- Composite measure of all-cause mortality, MI, stroke (mRS≥1 and increase by ≥1 from baseline), or unplanned revascularization for ischemia occurring from the time of randomization up to study day 1095, as estimated by the Kaplan-Meier failure rate and analyzed using a Z statistic in the same way it is described under the Section 2.3.1, with a 1-sided alpha of 0.05 and a margin of 8.4%. All available data through 3-years of follow-up will be used. Days from the randomization date or the procedure date to the first occurrence of one of the events within this composite, an early withdrawal date, or the last follow-up date occurring by 3 years post randomization will be calculated for each patient. For patients

who dropped out early, but had a death date available per the national death registry, this date will be used in the calculation of days and counted as an event. If a patient does not have an event or an early withdrawal date:

- Days from randomization will be set to 1095 days (3 years) if their last follow-up date is known to occur after 3 years.
- The date of the last visit will be the date of the phone call, office visit or last medical contact.

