2.5.1 Primary Endpoint

The primary endpoint of all cause death, MI or stroke (mRS \geq 1 and increase by \geq 1 from baseline) occurring up to 3 years post randomization will be evaluated using the difference in Kaplan-Meier failure rates in the intent-to-treat population. For the primary endpoint, sample size calculations for the Com-Nougue approach¹, which utilizes the difference in Kaplan-Meier failure rate estimates, were derived using simulations. The Com-Nougue approach was very similar to that calculated using the asymptotic approach (difference \leq 0.5%). Therefore, the asymptotic test was used to approximate the power for the Com-Nougue approach using PASS 2008 (NCSS, LLC. Kaysville, Utah)³.

The hypothesis test is designed to show non-inferiority of PCI to CABG for the primary endpoint via the Z statistic, which is a normal approximation to the Binomial, with a one-sided alpha of 0.025. The null (H_0) and alternative (H_A) hypotheses are:

```
H0: F_{PCI-PE}(T) - F_{CABG-PE}(T) \ge \Delta_{PE}
```

```
HA: F_{PCI-PE}(T) - F_{CABG-PE}(T) < \Delta_{PE}.
```

 F_{PCI-PE} and $F_{CABG-PE}$ are the Kaplan-Meier estimates of failure rate of the primary endpoint at 3 years in the PCI and CABG arms, respectively. Δ_{PE} is the non-inferiority margin for the primary endpoint.

The sample size calculation is based on the following assumptions:

- primary endpoint event rate is 11% in each treatment arm at 3 years (using 3-year event rates from the SYNTAX trial, the most contemporary reference dataset)
- minimum time to follow-up is 2 years
- median time to follow-up is approximately 3 years
- 8% lost to follow-up at 3 years
- non-inferiority margin $\Delta_{\text{PE}} = 4.2\%$
- one-sided alpha = 0.025
- accrual time of 29 months.

A sample size of 1,900 subjects (950 per arm) will provide approximately 80% power to

demonstrate non-inferiority of PCI to CABG.

If non-inferiority is met, superiority testing will be performed with a one-sided alpha of 0.025. The null (H_0) and alternative (H_A) hypotheses for the superiority test are:

H₀: $F_{PCI-PE}(T) - F_{CABG-PE}(T) \ge 0$

H_A: $F_{PCI-PE}(T) - F_{CABG-PE}(T) < 0$.

Using a one-sided alpha of 0.025, assuming 8% lost to follow-up at 3 years, the trial will have approximately 80% power to demonstrate superiority with a difference of 3.84% of PCI to CABG (e.g. 7.16% in the PCI arm vs. 11% in the CABG arm).

2.5.2 Major Powered Secondary Endpoints:

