2.6 JUSTIFICATION OF DELTA

The non-inferiority margin of 4.2% for the primary endpoint is for the difference between the cumulative event rates at 3 years. For the PCI arm to pass the non-inferiority test for the primary endpoint of the composite of death, MI and stroke at 3 years, the maximum allowable event rate would be approximately 12.1%. Compared to the 11% event rate of the CABG arm, the average difference per year is approximately 0.4%. The criteria for an acceptable non-inferiority delta was carefully considered by the principal investigators, executive committee, PCI and surgical committees and country leaders of this protocol, representing more than 100 physicians not related to the study sponsor, 50% of whom are interventional cardiologists and 50% of whom are cardiac surgeons. A non-inferiority margin of 4.2% for the primary endpoint in this protocol has been agreed upon by this balanced study leadership to represent clinical therapeutic interchangeability between PCI and CABG, given the substantially lower peri-procedural morbidity of PCI, the likelihood for fewer strokes with PCI, especially in the first 30 days to 1 year (which in most cases is a clinically more important endpoint than MI, although the trial will not be powered to demonstrate a reduction in stroke), and the likely higher rate of subsequent unplanned revascularization for PCI.

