2.7 STUDY SUCCESS

Study success is defined as passing the non-inferiority test of PCI to CABG on the primary endpoint of all cause death, MI or stroke (mRS \geq 1 and increase by \geq 1 from baseline) at 3 years. Detail of the test is specified in sections 2.5.1.

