3.2 Analysis of the Primary Endpoint

The primary analysis for non-inferiority and superiority will use the Kaplan-Meier estimates defined from randomization date. A sensitivity analyses for superiority will also be performed where time is defined from randomization. Additional sensitivity analysis for the same non-inferiority and superiority test mentioned above will be rerun changing the start date from randomization to procedure date. The stop date for all analyses defined at 3 yeatrs will be 1095 days from randomization.

Primary and supplemental analyses are defined below.

- 1. Primary Analysis of the Primary Endpoint for non-inferiority: Code for the primary analysis testing for non-inferiority with 1-sided alpha = 0.025, the non-inferiority margin $\delta = 4.2\%$.
 - Run the product-limit model:

```
Proc lifetest data = DATAXX method = pl cs=none atrisk
```

```
timelist = 1095 outsurv = OUTSURV ;
```

Time Timevar*Censvar(0);

strata/ Group = treatment test = logrank;

Run;

- Use results in OUTSURV to compute formula in 2.3.1. Reject Ho if the critical value $< -Z_{1-\alpha}$
- 2. Primary Analysis of the Primary endpoint using Z test for Superiority: Code for the primary endpoint testing for superiority with 1-sided alpha = 0.025: same as above, only use $\delta = 0$ in calculations. This will be the primary test for superiority.
- 3. Sensitivity Analysis using Cox Model for Superiority: The primary endpoint is tested for superiority with 1-sided alpha = 0.05 using a Cox proportional hazards model. The proportional hazard assumption will first be tested by plotting the log-negative-log survival curves vs the log of survival time for each level of treatment group.

If it is determined that the proportional hazard assumption is violated, then a logistic regression will be performed adjusting for time of follow-up in each group.

Code to Test Proportional Hazard Assumption:

proc lifetest data=DATAXX plot=(lls) noprint; time Timevar*Eventvar(0); strata Group; run; Code for Cox model where Proportion Hazard Assumption is **Not** violated: ods output ParameterEstimates=*Out1*; Proc phreg data = DATAXX ; model Timevar*Eventvar (0) = Group / rl; run;

Summary tables for time to event endpoints will include failure rates (Kaplan-Meier estimates), unadjusted hazard ratios, confidence interval for the hazard ratio, and a p-value.

```
Code for Logistic Regression used when Proportional Hazard Assumption is violated:

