3.3 Analysis of the Powered Secondary Endpoints

- The first powered secondary endpoints, the KM estimate of the composite rate of allcause mortality, MI or stroke (mRS≥1 and increase by ≥1 from baseline) from randomization to 30 days post randomization, will be analyzed in a similar fashion as the primary analysis of the primary endpoint described in Section 3.2 above. The key differences are that a 1-sided alpha is set at 0.05 and only non-inferiority will be tested at a margin of 2%.
- The second powered secondary endpoint is the KM estimate of the composite rate of all cause mortality, MI, stroke (mRS≥1 and increase by ≥1 from baseline) or unplanned revascularization at 3 years. The same analysis will be performed as described for the primary anaylsis of the primary endpoint except the non-inferiority margin = 8.4%

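### The Z statistic, cut-off and p-value in SAP 2.3.1 and 3.2 contradict each other and the SAP's own hypotheses, leaving three incompatible criteria for non-inferiority of PCI

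*SAP*

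**What the plan says.** The direction of the test is stated correctly in several places. SAP 2.5.1 and Protocol 9.1.6.1 give H_A as F_PCI − F_CABG < Δ with Δ = 4.2% and one-sided alpha 0.025. SAP 3.4.4 notes that a higher rate is worse and declares non-inferiority when the upper one-sided bound of the difference is below Δ. SAP 2.6 says that for PCI to pass, "the maximum allowable event rate would be approximately 12.1"%, against 11% for CABG.

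The computing instructions differ:

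- SAP 2.3.1 defines the numerator as "Z = \frac{F_{CABG}(T) - F_{PCI}(T) - \delta", divided by the Greenwood standard error, with "P-value = 1- probnorm(Z").
- SAP 3.2 tells the analyst to compute the 2.3.1 formula and then: "Reject Ho if the critical value $< -Z_{1-\alpha". For superiority it repeats this with delta set to 0.
- SAP 2.3.2 carries the formula to the 30-day endpoint: "These KM estimates will be put into the Z statistic defined in Section 2.3.1 using a margin of 2% to test for non-inferiority". It treats the 3-year endpoint with revascularization in the same way. SAP 3.3 analyses both secondaries like the primary, and for the 30-day endpoint adds that "only non-inferiority will be tested at a margin of 2"%.

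On which text governs, SAP 2.7 defines study success as passing the primary test and says "Detail of the test is specified in sections 2.5.1". Section 2.5.1 says "The hypothesis test is designed to show non-inferiority of PCI to CABG for the primary endpoint via the Z statistic" but prints no formula for Z. SAP 3.4.4 refers decision rules back to the endpoint analysis sections. SAP section 5 records no change of direction from the protocol.

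**The concern.** One test statistic cannot serve both the 3.2 cut-off and the 2.3.1 p-value, because rejecting when Z is very negative and obtaining a small p when Z is very positive are opposite tails. Neither agrees with the hypotheses once delta is subtracted from CABG minus PCI. As written, the rule in the section that gives the primary analysis code passes PCI more surely the worse PCI does.

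The test that defines study success therefore cannot be programmed and reported as it stands, and someone would have to choose among criteria after the SAP is final. The problem reaches every confirmatory test in SAP 3.10: primary non-inferiority, primary superiority and both powered secondaries.

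**Working it through.** **Inputs.** From SAP 2.5.1: 11% per arm, δ = 0.042, one-sided alpha 0.025 (z = 1.96), 950 per arm, 8% loss. From 2.5.2: 30-day rate 3%, δ = 2%; 3-year composite 22%, δ = 8.4%; both at alpha 0.05 (z = 1.645). Assumption: an unpooled binomial SE stands in for Greenwood, with 950 × 0.92 = 874 per arm for the 3-year endpoints and 950 for the 30-day endpoint.

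**Reproducing the plan's power.** SE = √(2 × 0.11 × 0.89 / 874) = 0.01497. Power = Φ(0.042/0.01497 − 1.96) = Φ(0.846) = 80.1%, matching the stated 80%. The required n is 872 per arm, or 948 after 8% loss, against the planned 950.

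**The three criteria, solved for D = F_PCI − F_CABG.**

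- (A) SAP 3.4.4: D + z·SE < δ, so D < δ − z·SE.
- (B) SAP 3.2: (−D − δ)/SE < −z, so D > −δ + z·SE. This is the test that CABG is non-inferior to PCI.
- (C) SAP 2.3.1 p < 0.025: (−D − δ)/SE > z, so D < −δ − z·SE. This is the test that PCI is better by more than the margin.

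With SE = 0.01497, z·SE = 0.0293, so the limits are A: D < +1.27 points; B: D > −1.27 points; C: D < −7.13 points.

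**Observed PCI rate that passes, CABG observed at 11%** (SE re-evaluated at each PCI rate):

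| n per arm | A (3.4.4) | B (3.2) | C (p-value) | 3.2 superiority, δ = 0 |
|---|---|---|---|---|
| 817 | ≤ 12.10% | ≥ 9.76% | ≤ 4.25% | ≥ 14.22% |
| 874 | ≤ 12.20% | ≥ 9.65% | ≤ 4.33% | ≥ 14.10% |
| 950 | ≤ 12.31% | ≥ 9.53% | ≤ 4.42% | ≥ 13.97% |

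The value 817 is the n at which A equals the SAP's own 12.1% ceiling.

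**Probability of declaring PCI non-inferior, true CABG rate 11%, n = 874:**

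| True PCI | A | B | C |
|---|---|---|---|
| 7.16% | 99.995% | 4.5% | 1.3% |
| 11% | 80.1% | 80.1% | about 0 |
| 12.1% | 52.7% | 93.4% | about 0 |
| 15.2% (null boundary) | 2.5% | 99.9% | about 0 |

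A and B coincide at equal rates, so the power calculation does not reveal the error. If both arms are observed at 11%, Z as written is −0.042/0.01497 = −2.81: 3.2 rejects H0 while the printed p-value is 1 − Φ(−2.81) = 0.997.

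**Superiority, δ = 0.** At the planned 7.16% vs 11%, the 3.2 rule succeeds with probability 9.7 × 10⁻⁷ and the p-value rule with probability 80.0%. At PCI 15.2% vs 11%, the 3.2 rule declares PCI superior 74.1% of the time. Here the p-value is right and the cut-off is wrong, with no margin involved.

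**Secondaries at their null boundaries under the 3.2 rule.**

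- 30-day (PCI 5%, CABG 3%, n = 950): SE = 0.00898, mean Z = −0.04/0.00898 = −4.45, P(Z < −1.645) = 99.8%, against a nominal 5%.
- 3-year with revascularization (30.4% vs 22%, n = 874): SE = 0.02094, mean Z = −0.168/0.02094 = −8.02, probability about 100%, against a nominal 5%.

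**The case against.** The strongest reply is that nobody could mistake the intent. The hypotheses in 2.5.1 and 2.5.2, the ceiling in 2.6, the bound in 3.4.4, the testing sequence in 3.10 and the protocol all point the right way, and a printed p of 0.997 beside a rejection would expose the slip at once. That stands. The 99.9% figure is what literal coding of one line would give and does not estimate the trial's likely error rate. It does not make the written test usable: a SAP exists to fix the rule in advance, and it states no precedence among the three.

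A second reply is that 3.4.4 already supplies a complete, correct cut-off. It does, but it hands decision rules to the endpoint sections, and the only Z formula and Z cut-off are in 2.3.1 and 3.2.

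A lost plus sign in the PDF would not rescue the text. With +δ the p-value would match H_A (Z = 2.81, p = 0.0025 at equal rates), but 3.2 would still use the opposite tail, and the superiority conflict has no delta in it.

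Staggered entry makes the Greenwood variance larger than the binomial one at 874. Assuming uniform accrual over 29 months, a 24-month minimum and exponential events and losses, the effective n is about 824, near the 817 row. Thresholds move by about 0.1 point and no conclusion changes.

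Finally, 3.4.4 speaks of superiority tests for the powered secondaries as well; 2.5.2 and 3.10 limit them to non-inferiority, and that reading is used here.

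**Conclusion.** The concern holds. SAP 2.3.1 and 3.2 contain a wrong sign on delta and a wrong tail, so the SAP gives three criteria for its primary test that disagree on the same data. Only 3.4.4 agrees with the hypotheses. With CABG observed at 11%, the passing region for PCI is at most about 12.2%, at least about 9.7%, or at most about 4.3%, depending on which text is followed.

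The sizes rest on a normal approximation with 874 per arm (817 to 950 shown); the direction of the error does not depend on n. Hypotheses, margin, alpha and sample size are unaffected, and nothing here shows that the analysis was programmed wrongly. It must be corrected because it is the rule that decides study success.

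**What to change.** 1. In SAP 2.3.1, set Z = (F_CABG(T) − F_PCI(T) + δ)/SE and keep p = 1 − probnorm(Z).
2. In SAP 3.2, reject H0 if Z > z(1−α). Use δ = 0 for superiority, on the primary endpoint only.
3. State that this is equivalent to the bound in 3.4.4. The interval printed in 2.3.1 is for CABG minus PCI, so either re-express it as PCI minus CABG or state the rule as lower limit > −δ. Applying the 3.4.4 wording (upper bound below Δ) to the interval as printed would reproduce the wrong-direction rule.
4. In SAP 2.7, cite 2.3.1 and 3.2 alongside 2.5.1.
5. Minor: with z(1−α) the 2.3.1 interval is 95% two-sided at alpha 0.025, but 90% if reused for the secondaries at alpha 0.05. Label it so, or use z(0.975).

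After the change, Z, p-value and bound agree: 80.1% power at equal rates, 2.5% type I error at 15.2% vs 11%, and a PCI ceiling of 12.2% (12.1% at the lower effective n). The cost is one sign, one inequality, one cross-reference and a sentence on the interval, with no new data and no design change.
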